18.	Development of a new product/process or the generation of intellectual property	31
19.	References	32
20.	Appendices	34
20.1	Vitamin D Supplementation	34

**University of
Nottingham**
Health Service

3. Plain English Summary

Vaccines help us prevent diseases and keep us well. Some vaccines work better than others and there are many reasons for this. It can be to do with the vaccine itself or to do with the person having the vaccine. We have already found that people who report feeling happier on the day they are vaccinated produce more antibodies in response to the vaccination. We have also found that giving people only 15 minutes of a positive mood intervention to watch before they are vaccinated improves their mood. Recent research also suggests that the amount of vitamin D in your body at the time of vaccination can affect how well vaccines work.

In this study we will conduct a small experiment in which people who are about to receive a COVID-19 or influenza vaccination, or both, will be put in one of 4 groups at random.

- Group 1 will not be offered anything other than their vaccine (this is called usual care).
- Group 2 will receive a brief positive mood intervention, which has previously been shown to improve mood on the day they are vaccinated and for a further 6 days. They will also be advised to take a single dose of a vitamin D tablet just before they are vaccinated and once daily for the following 27 days.
- Group 3 will also receive the positive mood intervention on the day they are vaccinated and for a further 6 days, but they will not take the vitamin D tablet.
- Group 4 will be advised to take a vitamin D tablet at the time of vaccination and once daily for the following 27 days.

We will ask all participants to provide 15ml blood samples before vaccination and then at 28 days and at 6 months post vaccination. This sample will help us measure antibody responses to the vaccination and determine how well people have responded. In addition, up to 20 people across all groups will be asked to provide up to a 60ml blood sample at baseline and at day 28. These samples will allow us to understand how our interventions are changing the way the immune system works.

Finally, we will also interview a small number of participants as well as people working in vaccine clinics to gain their views on our approach to improving vaccine effectiveness. This work will help to identify if there is an easy and effective way to make vaccines work better that is acceptable to doctors and patients, doesn't have any side effects and which anyone, anywhere can try.

4. Synopsis

Study title	A feasibility randomised controlled trial examining the effect of a positive mood intervention and vitamin D supplementation on the immunological responses to a boosting COVID-19 and/or influenza vaccination in healthy adults		
IRAS reference	316876		
Short title	PROTECTIVE-D: imPROving the effecTivenEss of vaccinaTion wltH positive mood and Vitamin D		
Participants	Adults aged 65 years and over eligible for COVID-19 booster vaccination in Autumn 2022		
Sample size	~40		
Treatment	Positive mood intervention +/- vitamin D supplementation		
Treatment duration	7-28 days		
Study duration	12 months		
Planned study period	November 2022 to November 2023		
Objectives	Outcome measures	Evaluation time points	
Primary	Feasibility and acceptability of study interventions for testing in future studies	Qualitative assessment of acceptability of interventions. Intervention adherence measures.	4 weeks

**University of
Nottingham**
Health Service

Exploratory	Assessment of effectiveness of study intervention in improving immune response to COVID-19 boosting and/or influenza vaccination.	Anti-SARS-CoV-2 immunoglobulin levels +/- vaccine induced influenza immunoglobulin levels	4 weeks 24 weeks
	Further investigate immunological response to intervention.	SARS-CoV-2/influenza neutralising antibodies and T-cell responses.	4 weeks

**University of
Nottingham**
Health Service

5. Abbreviations

AE:	Adverse Event
AR:	Adverse Reaction
CI:	Chief Investigator
CRF:	Case Report Form
CTIMP:	Clinical Trial of Investigational Medicinal Product
DSUR:	Development Safety Update Report
EudraCT:	European Clinical Trial Database
FDA:	Food and Drug Administration
GCP:	Good Clinical Practice
GDPR:	General Data Protection Regulation
HRA:	Health Research Authority
ICF:	Informed Consent Form
ISF:	Investigator Site File
PI:	Principal Investigator
PIS:	Participant Information Sheet
PPI:	Patient and Public Involvement
REC:	Research Ethics Committee
SAE:	Serious Adverse Reaction
SAE:	Serious Adverse Event
SOP:	Standard Operating Procedure
SUSAR:	Suspected Unexpected Serious Adverse Reaction
UNHS:	University of Nottingham Health Service

**University of
Nottingham**
Health Service

6. Background and rationale

Vaccines play a critical role in reducing the burden of infectious disease in the population. However, with all vaccines there is variability in the effectiveness and durability of protection, with the greatest variability evident in older people. Previous research has shown that a range of emotional and lifestyle factors alter vaccine effectiveness including positive and negative mood^{1,2} and vitamin D status³ and that interventions which target these factors can enhance vaccine success⁴. Furthermore, there is evidence that vitamin D and negative mood may be inversely related, suggesting that an intervention which combines both adjuvants may have synergistic effects.

The proposed project would build on existing evidence which has demonstrated the benefits of positive mood and vitamin D for vaccine effectiveness. The aims would be to:

1. Adapt an existing brief single session positive mood intervention to permit delivery of multiple sessions in the seven days post-vaccination
2. Assess the feasibility and acceptability of vitamin D supplementation for 28 days and a brief positive mood intervention for 7 days in older adults.
3. Gather preliminary evidence on the effects of positive mood alone, vitamin D alone and positive mood and vitamin D in combination on the antibody response to influenza and SARS-CoV-2 virus vaccines
4. Investigate the cellular and humoral immune mechanisms mediating intervention effects

**University of
Nottingham**
Health Service

7. Methods

Patients aged 65 years or greater being targeted for COVID-19 and/or influenza vaccination will be recruited from primary care to participate in a feasibility trial. They will be randomly allocated on a 1:1:1:1 basis to receive:

- No intervention (Usual Care)
- Positive mood intervention on the day of vaccination and for the following 6 days and vitamin D supplementation on the day of vaccination and once daily for the following 27 days
- Positive mood intervention on the day of vaccination and for the following 6 days
- Single dose oral vitamin D supplementation on the day of vaccination and once daily for the following 27 days

15 ml venous blood samples will be collected to detect antibodies to the vaccine antigens. These will be measured at baseline, 4 weeks and 6 months post-vaccine to assess intervention effects on peak vaccine responses and durability of protection. Participants will also receive a daily text message reminder with a link to the positive mood intervention and/or to take their vitamin D supplement, alongside an e-diary link to complete.

A sub-sample of up to 20 patients will be invited to have blood samples collected to explore potential cellular and humoral mechanisms at day 0 and day 28. This will entail an additional maximum 60ml blood sample on each occasion.

Interviews will be conducted with patients and health care professionals involved in the pilot trial to identify barriers and facilitators to implementing the intervention in routine care.

8. Participant identification

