9.3 Enrolment visit

- Informed consent and eligibility will be checked by the research team (PIs, research nurse or practitioner).
- Demographics and medical history will be collected.
- Participants will be randomly allocated to one of the 4 study groups in a 1:1:1:1 ratio.
- Randomisation will be performed by an electronic randomisation system.
- Participants will provide a 15ml venous blood sample for biochemical and immunological analysis. A subgroup of participants will be invited to have a maximum 60ml blood sample taken for further immunological analysis. Venous blood samples will be collected by a phlebotomy trained Research Nurse/Practitioner using a vacutainer system or syringe and butterfly.
- Participants randomised to the positive mood intervention will receive a 15 minute positive mood intervention consisting of a combination of positive mood stimuli previously shown to enhance mood in older adults. Participants will also receive information on how to access their positive mood intervention over the next 6 days. Daily reminders to complete the intervention and e-diary will be sent via secure SMS messaging and checked by the PI and/or Research Nurse. In the event a participant is unable to work the e-diary, alternatives can be provided, such as paper copies or phone calls.
- Participants randomised to standard over the counter vitamin D supplement, will be advised to buy and take this immediately prior to vaccination and once daily for the following 27 days. Reminders will be sent to complete the intervention and e-diary as for the positive mood intervention group.
- Participants will then receive their COVID-19 booster and influenza vaccination in the standard NHS clinic which will be running at the site on that day. The vaccine will not be given as part of the study and the type of vaccine, timing or method will not be impacted by their participation in the study.

Some participants, clinicians' and other stakeholders' will then be interviewed about the intervention and trial acceptability and determine the barriers and facilitators to implementing the intervention in routine care. Interviews will be conducted by telephone, video call or face-to-face at participant preference, audio-recorded (with permission) and transcribed verbatim.

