10.4 Safety reporting procedures

SAEs and AESIs will be reported to the CI as soon as possible after being reported to a member of the team. The CI will be responsible for deciding whether the participant is able to continue the study; whether the study can continue; and whether the sponsor should be informed.

Assignments of causality will only be made in relation to the administration of Vitamin D and/or positive mood intervention during the study. Any SAEs which occur following externally administered vaccines or medicines e.g., those given as part of the patient's usual care, will be judged to be unrelated to the study vaccine and should additionally be reported through national pharmacovigilance mechanisms as applicable.

Hospitalisation (including inpatient or outpatient hospitalisation for an elective procedure) for a pre-existing (existing prior to administration of Vitamin D during the study) condition that has not worsened unexpectedly does not constitute an SAE. Emergency department attendances should not routinely be reported as SAEs unless they meet the SAE definition described above.

The procedure for reporting of Serious Adverse Events is to complete an SAE report form for all reportable SAEs. The CI or delegate will submit (in addition to the expedited reporting above) DSURs once a year throughout the clinical trial, or on request, to the Competent Authority (MHRA), Ethics Committee, HRA (where required), Host NHS Trust and Sponsor. The safety profile will be continuously assessed by the Investigators. The CI and relevant investigators (according to the study delegation record) will also review safety and SAE issues as they arise.

**University of
Nottingham**
Health Service

11. Statistics

Evaluation of the findings will be conducted by the study team using SPSS and overseen by the study statistician [name].

The main statistical analysis will be to identify a statistically significant difference in the four groups and identify any additional immune effect of vitamin D supplementation given at the time of vaccination. We will use a range of advanced techniques, such as multivariate statistical methods and advanced clustering and classification approaches to assess the independent and combined contribution of psycho-behavioural factors to immunological responses to the vaccination.

All validated measures employed will be summarised according to published guidelines.

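### The antibody outcome is stated as a post-vaccination level with no role for the measured baseline level, which costs precision and leaves the arm contrasts open to chance baseline imbalance at about 10 per arm

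*Protocol*

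**What the plan says.** The synopsis (section 4) lists as an exploratory objective "Assessment of effectiveness of study intervention in improving immune response to COVID-19 boosting and/or influenza vaccination". The outcome measure set against it is "Anti-SARS-CoV-2 immunoglobulin levels +/- vaccine induced influenza immunoglobulin levels", and the evaluation time points are "4 weeks 24 weeks". Baseline is not among them, and no change, fold-rise or baseline-adjusted form is given.

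Section 7 (Methods) says of the antibodies: "These will be measured at baseline, 4 weeks and 6 months post-vaccine to assess intervention effects on peak vaccine responses and durability of protection". Sections 9.3 and 9.4 confirm a blood sample from every participant at visit 1, day 28 and day 168.

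Section 11 (Statistics) says "The main statistical analysis will be to identify a statistically significant difference in the four groups" and adds "We will use a range of advanced techniques, such as multivariate statistical methods and advanced clustering and classification approaches". It names no covariate. Randomisation is described in section 9.3 only as "Participants will be randomly allocated to one of the 4 study groups in a 1:1:1:1 ratio", by an electronic system, with no stratification factor stated. Section 11.1 sets a minimum of 10 per arm before a pause, and 20 per arm if recruitment resumes.

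**The concern.** The participants are "Adults aged 65 years and over eligible for COVID-19 booster vaccination in Autumn 2022" (section 8.1 extends this to 2023), and prior infection is not an exclusion. Many will therefore already have antibody to the vaccine antigens before visit 1, in differing amounts. Part of what is measured at day 28 was then present beforehand. The objective concerns response, but the level at follow-up mixes what the vaccination added with what was already there.

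The information that separates the two is collected from everyone and has no stated use in the outcome or the comparison. With about 10 per arm and unstratified allocation, appreciable chance differences in baseline antibody between arms are common. A comparison of levels passes part of any such difference into the estimated intervention effect, and it leaves in the residual variance a component that the baseline value could remove. At stake is how informative the preliminary evidence sought under aim 3 in section 6 will be.

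**Working it through.** **The plan's own figure.** 4 arms × 10 = 40 and 4 arms × 20 = 80, as section 11.1 states. No power, alpha, effect size or SD is given, so there is no power figure to reproduce.

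**Inputs.** n = 10 or 20 per arm (section 11.1). Equal allocation (section 9.3). Log antibody is expressed in SD units, with the same SD at baseline and follow-up. The correlation ρ between log baseline and log follow-up level is not in the protocol and is assumed to lie between 0.3 and 0.8.

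**Step 1: chance imbalance.** The SD of the difference in baseline means between two arms is √(2/n).
- n = 10: √0.2 = 0.447. P(|difference| > 0.5 SD) = 2 × [1 − Φ(0.5/0.447)] = 26%. By simulation (200,000 draws), at least one of the three active arms differs from usual care by more than 0.5 SD in 54% of trials, and at least one of the six pairs does so in 68%.
- n = 20: √0.1 = 0.316. The same three probabilities are 11%, 26% and 39%.

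**Step 2: carry-over.** A baseline imbalance of d shifts the expected difference in follow-up levels by ρ × d. For d = 0.5 SD this is 0.3 × 0.5 = 0.15 SD up to 0.8 × 0.5 = 0.40 SD.

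**Step 3: type I error of a comparison of levels.** Simulated two-arm t-test, n = 10, no true effect, 100,000 draws:

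| ρ | All randomisations | Imbalance > 0.5 SD | Imbalance ≤ 0.5 SD |
|---|---|---|---|
| 0.5 | 4.9% | 9.4% | 3.3% |
| 0.7 | 5.0% | 13.5% | 2.0% |

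The overall rate is held. The distortion is conditional on the imbalance that occurs.

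**Step 4: precision of the three possible analyses.** The difference detectable with 80% power at two-sided 5% is (1.960 + 0.842) × √(2/n) × k. Here k = 1 for the level alone, √(1 − ρ²) for the level adjusted for baseline, and √(2(1 − ρ)) for change from baseline. For n = 10:

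| ρ | Level alone | Adjusted level | Change | Power at 0.8 SD: level / adjusted / change |
|---|---|---|---|---|
| 0.3 | 1.253 | 1.195 | 1.482 | 43% / 47% / 33% |
| 0.5 | 1.253 | 1.085 | 1.253 | 43% / 54% / 43% |
| 0.7 | 1.253 | 0.895 | 0.970 | 43% / 71% / 64% |
| 0.8 | 1.253 | 0.752 | 0.792 | 43% / 85% / 81% |

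The ratio of confidence interval widths, adjusted to unadjusted, is √(1 − 0.25) = 0.87 at ρ = 0.5 and √(1 − 0.49) = 0.71 at ρ = 0.7, a narrowing of about 13% and 29%. The formula ignores the small loss from estimating the slope. At n = 20 the detectable differences are 0.886 SD for the level alone, and 0.767 SD (ρ = 0.5) and 0.633 SD (ρ = 0.7) after adjustment.

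**Step 5: change from baseline.** It matches the level alone at ρ = 0.5, is worse below that, and is less precise than the adjusted level at every ρ shown. It also over-corrects an imbalance of 0.5 SD, by (1 − ρ) × 0.5: 0.35 SD at ρ = 0.3 and 0.10 SD at ρ = 0.8.

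**The case against.** The strongest reply is that the protocol is silent on baseline and does not exclude it. Section 7 names baseline among the measurements that serve the assessment of vaccine responses. The plain English summary (section 3) treats the samples before and after vaccination as the means of judging how well people responded. The definition of compliance in section 9.7 requires a sample from each side of vaccination. The choice of covariates commonly belongs in a statistical analysis plan, and that plan is not at hand. All of this stands. A reader might infer that the protocol deliberately substitutes level for response, but the text does not support that. What remains is that the outcome and its time points are stated in the protocol, and neither there nor in section 11 does the baseline value have a role.

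A second reply is that randomisation protects the comparison. It does. A reader might infer that a comparison of levels is biased or inflates false positives, but step 3 shows the overall rate stays near 5%. The cost is lost precision, together with distortion in the particular trial where arms are unbalanced.

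A third is that referring each person to their own baseline by a change score may do harm. That is correct at low correlation (step 5), so the remedy has to be adjustment and not a change score.

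Two further inferences should be resisted. One is that the day-28 level is mostly carried over from before vaccination: at ρ of 0.5 to 0.7, baseline explains 25% to 49% of its variance, which is less than half. The other is that the larger trial would inherit a wrong variance: section 11.1 ties the design of that trial to acceptability and to how well adherence is captured, and mentions no antibody variance.

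**Conclusion.** The point holds as a missed improvement in how the antibody outcome and its comparison are stated. The level at 4 and 24 weeks is the only form given, and the measured baseline has no stated use. At 10 per arm a baseline imbalance above 0.5 SD has a 26% chance for any one pair of arms, and it would move that contrast by 0.15 to 0.40 SD. Adjustment would narrow confidence intervals by about 13% to 29% at correlations of 0.5 to 0.7. The imbalance probability depends only on n and approximate normality. The shift and the gain in precision also rest on assumed correlations and on equal SDs at the two times.

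The weight is moderate. The outcome is exploratory and the trial is a feasibility study without a powered comparison. Against that, section 11 makes a between-group difference its main analysis, and the improvement uses data already being collected.

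**What to change.** In the synopsis and section 11, state the antibody outcome, separately for each vaccine antigen, as the log-transformed level at day 28 and at day 168. State that it is compared between arms with adjustment for that participant's log baseline level for the same antigen. The geometric mean fold-rise from baseline may be reported beside it as a description, but it should not replace the adjusted comparison.

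The change is one of wording. No visit, blood draw or assay is added. The only cost is that participants without a baseline value drop out of the adjusted estimate, since section 11.2 rules out imputation. They should be few, because the sample is taken at visit 1 before vaccination.

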8.1 Study participants

Adults aged 65 and over who will be receiving an invitation to a COVID-19 or COVID-19 and influenza vaccination appointment at their GP Practice and/or mass vaccination clinic as per UK government guidance in autumn **2022 or 2023** will be eligible to participate in this study.

8.2 Inclusion criteria

- Participants must be able and willing to provide written informed consent to participate in the study.
- Participants must be able and willing (in the investigator's opinion) to comply with all the study requirements.
- Participants must consent to allow investigators to discuss their medical information with their general practitioner and access medical records where relevant to the study.
- Eligible to receive a COVID-19 vaccination and/or influenza vaccination as part of usual care.

8.3 Exclusion criteria

- Participants who have enrolled on a COVID-19 vaccine clinical trial of investigational medicinal product (CTIMP) in the last 12 months.
- Participants who are clinically extremely vulnerable and received a third or fourth dose in Spring 2022.
- Those aged less than 65.
- Those ineligible to receive a COVID-19 and/or influenza vaccination as part of usual care or those for whom a COVID-19 and/or influenza vaccination is contraindicated.
- Those for whom the collection of blood samples is contraindicated.
- Deemed by health care provider to be:
 - Too physically frail to participate.
 - Diagnosed with dementia or other cognitive condition which would make participation difficult.
 - Insufficient command of English language to complete surveys and provide informed consent.
- Participants who, in the past 3 months, have been prescribed oral vitamin D supplementation by a health care professional or who take over the counter supplements regularly on the advice of a health care professional.

9. Study Design

This study aims to evaluate the feasibility of large-scale testing of the intervention in future trials by evaluating its acceptability to participants and adherence markers. Samples will be taken at various timepoints during the study and Adverse Events, Severe Adverse Events and Adverse Events of Special Interest will be recorded. Figure 1 below displays the activities for the study.

[figure not shown]

Figure 1 displays a flow chart of the proposed study design.

**University of
Nottingham**
Health Service

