9.9 Definition of end of study

The end of the study will be defined as the time the last blood sample is analysed.

10. Safety reporting

Safety reporting for participants in this study begins at the point of consent and ends at 168 days post-enrolment. Safety data will be collected via:

- Direct notification by the participant to the investigator via email or telephone according to the information on the study contact card given to each participant at enrolment.
- Investigator review of primary care medical records at 28 days and 168 days.

All serious adverse events that have not resolved by the end of the study, or that have not resolved upon discontinuation of a subject's participation in the study, must be followed until any of the following occurs:

- The event resolves
- The event stabilises
- The event returns to a baseline if a baseline value is available
- The event can be attributed to agents other than to study interventions or to factors unrelated to study conduct
- It becomes unlikely that any additional information can be obtained (participant or health care practitioner refusal to provide additional information, lost to follow-up after demonstration of due diligence with follow-up efforts)

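### Section 8.3 excludes contraindications to the usual-care vaccine and to blood sampling, but not to the vitamin D that the trial assigns to half its participants

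*Protocol*

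**What the plan says.** Protocol section 8.3 uses contraindication as a ground for exclusion twice. It excludes "those for whom a COVID-19 and/or influenza vaccination is contraindicated", and it excludes "Those for whom the collection of blood samples is contraindicated". Its one criterion on vitamin D concerns prior use: people who, in the past 3 months, "have been prescribed oral vitamin D supplementation by a health care professional", or who regularly take an over-the-counter supplement on professional advice.

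Section 7 randomises 1:1:1:1 to four arms, two of which include vitamin D on the day of vaccination and daily for 27 further days. Under section 9.3 these participants "will be advised to buy and take this immediately prior to vaccination and once daily for the following 27 days". The same section states that the vaccine is given in the ordinary NHS clinic and is not part of the study. Section 10.4 limits attribution accordingly: "Assignments of causality will only be made in relation to the administration of Vitamin D and/or positive mood intervention during the study".

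The more general provisions are these:

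- Section 8.2 asks for the investigator's opinion that the participant is able and willing "to comply with all the study requirements", and secures consent to consult the GP and the medical record.
- Section 9.3 has the research team check eligibility, and lists ahead of allocation: "Demographics and medical history will be collected".
- Section 10 provides for "Investigator review of primary care medical records at 28 days and 168 days".
- Appendix 20.1, on vitamin D, consists of a link to an NHS web page.

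**The concern.** The protocol screens for contraindications to something the patient would receive anyway, but not to the one ingested product the trial assigns. A person can meet every inclusion criterion, trigger no exclusion, and be allocated a supplement that is contraindicated for them.

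The way vitamin D is supplied removes a possible second check. The participant buys it, so the protocol describes no dispensing step. Consent, randomisation and the first dose all fall within visit 1. If informal judgement before allocation misses a contraindication, the next scheduled look at the medical record comes after the full course.

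There is also a smaller design cost. A contraindication found after allocation leads to stopping treatment only in the vitamin D arms, and section 9.8 does not replace participants who withdraw. Intervention adherence is a primary outcome measure, so someone who rightly stops vitamin D could be counted as non-adherent. The trial is meant to inform a larger one, and the gap could be carried into it.

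**Working it through.** The protocol gives no figure to reproduce on this point. The check is a comparison of the criteria, with simple arithmetic on exposure and timing.

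**Criteria side by side (sections 8.2 and 8.3)**

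| Procedure or product | Assigned by randomisation? | Who receives it | Contraindication excluded? |
|---|---|---|---|
| COVID-19 and/or influenza vaccine | No, usual care | All arms | Yes |
| Blood sampling | No, study procedure | All arms | Yes |
| Vitamin D | Yes | Two of four arms | No, prior use only |

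**Share exposed (sections 7 and 11.1)**

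- Two arms of four at 1:1:1:1: 2/4 = 50%.
- At a minimum of 10 per arm: 2 × 10 = 20 of about 40.
- At a minimum of 20 per arm, if recruitment resumes: 2 × 20 = 40 of about 80.
- Doses per participant: 1 (day 0) + 27 = 28.

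**Chance of allocation to vitamin D, given that k contraindicated people enrol**

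- Formula, treating allocations as independent: 1 − 0.5^k.
- k = 1: 1 − 0.5 = 0.50.
- k = 2: 1 − 0.5² = 0.75. With arms fixed at 10 each, 1 − (20/40)(19/39) = 0.756.

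These values follow from the allocation ratio and are conditional on k. The protocol gives no basis for estimating k.

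**Timing**

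- First dose: day 0, at visit 1, just before vaccination.
- Last dose: day 27.
- First timed record review: day 28. All 28 dosing days have passed by then.

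**Does another provision close the gap?**

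- The opinion required by 8.2 concerns ability and willingness to comply. A person with a contraindication may have both.
- The eligibility check in 9.3 applies the written criteria, which lack this item. Medical history is collected, but nothing says which finding would exclude.
- Section 9.6 measures serum vitamin D at each time point, but no eligibility rule uses the result.
- The link in Appendix 20.1 is not an eligibility criterion.
- The e-diary checks, the emergency telephone line and withdrawal under 9.8 act only once dosing has begun.

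None of these makes a vitamin D contraindication a ground for exclusion before randomisation.

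**Effect of one late discovery on a small arm:** 1 of 10 is 10% of that arm.

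**The case against.** The strongest reply is that the practical risk may be very small. The product is a standard over-the-counter supplement, the protocol states no dose, and the frequency of relevant contraindications among eligible people aged 65 and over cannot be found in it. The 50% and 75% figures only restate the allocation ratio. All of this stands, and it is why no overall risk is claimed.

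A second reply is that the safeguards are better than the criteria suggest. An investigator who knew of a contraindication could refuse entry under 8.2. The medical history is listed before allocation. Record access under 8.2 has no time limit, so the dates of the safety reviews do not show that records go unread at screening. The prior-use criterion already requires a question about vitamin D. Participants have at least 24 hours with an information sheet that must describe risks, and the daily reminders and e-diary mean that the dosing period is not unobserved. These points reduce the likely harm. They do not close the gap, because each depends on informal judgement, leaves the screening to the participant, or acts after the first dose.

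A third reply is that vaccination and blood sampling apply to every participant and produce the immune outcomes, so those exclusions have a purpose of their own. That is fair, and it weakens any inference that vitamin D was simply overlooked. It gives no reason to leave the assigned supplement without a safety criterion.

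**Conclusion.** The concern holds. Followed exactly as written, sections 8.2 and 8.3 admit a person for whom vitamin D is contraindicated, and that person has a 50% chance of being allocated 28 daily doses. The affected arms hold half of the participants.

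The conclusion rests on the text of the eligibility criteria and on the 1:1:1:1 allocation. It assumes nothing about which conditions are contraindications or how common they are. Eligibility belongs in the protocol, so an analysis plan that is not at hand would not supply the missing criterion.

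The gap is an omission that should be corrected. It is not evidence of harm, and no sample-size figure changes. Confidence is high that the criterion is absent; the size of the resulting risk is unknown.

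**What to change.** Add to section 8.3 an exclusion for people in whom vitamin D supplementation is contraindicated. The investigators should set the list of conditions from the product information.

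Check it for every participant before randomisation, whichever arm follows, so that all four arms are drawn from the same population. The medical history in 9.3 and the record access consented to in 8.2 already provide the means.

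The cost is one line in 8.3, one item on the eligibility checklist and a slightly narrower eligible pool.
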